MRI—this will be waived if subjects had an MRI performed at their outside hospital within 3 months of the 1st study visit and if subjects provide a CD of the images for review by our neuroradiologist to determine if of sufficient quality for a baseline study.

While on the drug, visits will occur once a month to monitor for adverse effects. Patients' visits may not deviate more than 7 days from the 30-day mark between each visit.

Visit 2: time 1 month on drug

Physical exam and history

Will draw CBC with differential, BMP, LFTs (15 cc blood)

For those with prolactinomas, will also check PRL.

For those with acromegaly from malignant tumors, will GH levels on 2 hour OGTT

For those with ACTH secreting malignant tumors, will check 24 hour urinary free cortisol

Do ECG

Urine Pregnancy Test

Those with pre-existing visual field compromise, visual field testing

Visit 3: time 2 months on drug

Physical exam and history

Will draw CBC with differential, BMP, LFTs (15 cc blood)

For those with prolactinomas, will also check PRL.

For those with acromegaly from malignant tumors, will check GH levels on 2 hour OGTT

For those with ACTH secreting malignant tumors, will check 24 hour urinary free cortisol

Those with pre-existing visual field compromise, visual field testing

Do ECG, echocardiogram

Urine Pregnancy Test

Visit 4: time of 3 months on drug

Physical exam and history

Will draw CBC with differential, BMP, LFTs (15 cc blood)

For those with prolactinomas, will also check PRL.

For those with acromegaly from malignant tumors, will check GH levels on 2 hour OGTT

For those with ACTH secreting malignant tumors, will check 24 hour urinary free cortisol

Pituitary hormones as well—TSH, thyroid panel, free T4, 8 am cortisol (if indicated), IGF-1, LH, FSH, testosterone (15 cc blood)

Tubes for lab for EGFR, her2 levels (10 cc blood)

Do ECG
Visual field test
Dilated retinal exam
Color Vision test
Do MRI of pituitary with and without IV gadolinium
Urine Pregnancy Test

Visit 5: time of 4 months on drug
Physical exam and history
Will draw CBC with differential, BMP, LFTs (15 cc blood)
For those with prolactinomas, will also check PRL.
For those with acromegaly from malignant tumors, will check GH levels on 2 hour OGTT
For those with ACTH secreting malignant tumors, will check 24 hour urinary free cortisol
Do ECG, echocardiogram
Urine Pregnancy Test

Visit 6: time of 5 months on drug
Physical exam and history

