Pregnancy Test for pre-menopausal women	X	X	X	X	X	X	X	X

^ Only for subjects with visual field deficits

^^ will be waived if subjects had MRI at outside hospital within 3 months of baseline visit

* Only for subjects with acromegaly from malignant tumors

+Only for subjects with ACTH secreting adenomas from malignant tumors

**Visit 8 is only required if stopping Lapatinib at visit 7. Patients continuing on Lapatinib after visit 7 will be followed by their physician as clinically appropriate.

Section 7.0 Assessment of Efficacy

a. Primary outcome variable.

Primary outcome in nonfunctioning pituitary adenomas: 40% reduction in tumor size in any dimension. Tumor size and volume will be calculated using Open Source OsiriX® Imaging Software for MacOS. MRIs will be performed at baseline and at 3 and 6 months All MRIs will be centrally read by the dedicated pituitary radiologist at CSMC.

Primary outcome in prolactinomas: 40% reduction in tumor size in any dimension.

Primary outcome in malignant pituitary tumors: Progression free survival

b. Secondary outcome variables.

Secondary outcomes in prolactinomas:

(a) achievement of 50% reduction of PRL levels (b) PRL normalization (c) percent reduction in PRL levels (d) percent reduction in tumor volume. Tumor volume will be calculated using Open Source OsiriX® Imaging Software for MacOS. (e) correlation of tumor size and PRL reduction (f) clinical predictors of TKI response, including age, gender, duration of disease, dose and duration of dopamine agonist therapy, baseline PRL, and baseline tumor size.

Secondary outcomes in malignant pituitary tumors: partial response, complete response, mortality, 24 hour urine free cortisol levels for Cushing carcinomas, IGF-1 levels for acromegaly carcinomas

We will correlate ErbB receptor expression with the subjects' clinical response to the study drug. This will be performed through immunohistochemistry staining of pituitary tumor slides from surgery.

Section 8.0 Assessment of Safety

1. *Monitoring for adverse effects (further detailed below):* Data has been collected on over 12000 subjects on combination therapy of lapatinib and other chemotherapies, and over 4000 subjects have been treated with lapatinib monotherapy, with 2347 of those specifically in breast cancer. With monotherapy, majority of AEs were Grade 1 or 2 in severity. The incidence of Grade 3 and Grade 4 events was 21% in those

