who received lapatinib and 7% in those on placebo. Risks of adverse events are not additive or cumulative. SAEs were reported in 6% of those on lapatinib compared to 5% on placebo. Cardiac events including left ventricular ejection fraction decreases were reported in approximately 1% of patients and most have partial or full recovery. Symptomatic decreases in ejection fraction were observed in approximately 0.3% of patients on lapatinib. Interstitial lung disease is observed in 0.2% of patients. Hepatotoxicity has been observed in <1% of patients. Grade 3 and 4 diarrhea occurs in <10% of patients. Nausea may be seen in 18% of patients and rash in 29% (Investigators' Brochure).

2. Prior to initiating therapy, patients will undergo an echocardiogram and ECG to evaluate the ejection fraction, and the echocardiogram will be repeated every 8 weeks and on visit. Patients will be evaluated for adverse effects monthly with physical examinations, chemistry and hematology panels, and ECGs. Adverse events will be graded by the NCI-CTC. Common adverse events include: hand-foot syndrome, rash, diarrhea, indigestion, nausea, vomiting, anorexia, anemia, low platelets, abnormal liver tests (ALT (SGPT) level raised, AST/SGOT level raised, hyperbilirubinemia, backache, pain in limb, insomnia, fatigue, and shortness of breath. Rare but serious events include: heart failure (depression of left ventricular systolic function), abnormal heart beat (prolonged QT interval), liver damage (hepatotoxicity), and lung problems (interstitial lung disease/pneumonitis). Lapatinib will be discontinued in those who developed decreased ejection fraction, who develop pulmonary symptoms. Those subjects with toxicity less than or equal to Grade 2 on the NCI-CTC will have their dose held and resumed when the toxicity has resolved. Those subjects with toxicity equal to Grade 3 on the NCI-CTC will have their dose held and resumed at a fifty percent dose reduction when the toxicity has resolved. Those subjects with toxicity equal to Grade 4 on the NCI-CTC will be discontinued on the study drug. [name], from Oncology department at Cedars-Sinai Medical Center, will assist us in monitoring patients for adverse events.
3. If at any time a patient demonstrates a worsening of their visual fields or tumor growth on MRI, they will be withdrawn from the study and referred for surgery.

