Overall, 45% of patients experience hepatic abnormalities on lapatinib and capecitabine. In a phase III trial of lapatinib monotherapy (n = 1573), 8% of patients experienced hepatobiliary events, 3% of those were SAEs. With lapatinib monotherapy, grade 3 hyperbilirubinemia has been reported in 2% of patients and grade 4 elevations in ALT/AST in 2%. Hepatotoxicity has been observed in <1% of subjects. Liver chemistry stopping and follow up criteria have been designed to assure subject safety and evaluate liver event etiology. All subjects who meet liver chemistry criteria requiring permanent discontinuation of investigational product must continue to be followed for the study assessments and procedures as defined in Section X and at the time points indicated in the Time & Events Table in Section X.

If a subject experiences ALT $>3 \times$ ULN and total bilirubin $>2.0 \times$ ULN ($>35\%$ direct; bilirubin fractionation required*), then the following actions must be taken:

immediately and permanently discontinue investigational product;
complete the SAE data collection tool, the liver event CRF, and the liver imaging and/or liver biopsy CRFs, if these tests are performed;
in addition to the liver event follow up assessments defined in Section X.X. below, the following are suggested: specialist or hepatology consultation; anti-nuclear antibody, anti-smooth muscle antibody, and Type 1 anti-liver kidney microsomal antibodies; and liver imaging and/or liver biopsy to evaluate liver disease;
promptly report the event to Novartis within 24 hours of learning its occurrence (refer to **'Reporting Serious Adverse Events section'** for guidance on prompt reporting to Novartis);
monitor every week until liver chemistries resolve, stabilize or return to within baseline values;
do not re-challenge with investigational product.

***NOTE:** bilirubin fractionation should be performed if testing is available. If testing is unavailable and a subject meets the criterion of total bilirubin $>2.0 \times$ ULN, then the aforementioned actions must still be performed.

If a subject experiences:

ALT $>8 \times$ ULN or
ALT $>5 \times$ ULN persisting for ≥ 2 weeks : retest within 3 days from the first occurrence and then weekly to determine if ALT elevation persists or
ALT $>3 \times$ ULN with signs or symptoms of hepatitis or hypersensitivity (the appearance or worsening of fatigue, nausea, vomiting, right upper quadrant pain or tenderness, fever, rash, or eosinophilia)

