Non-hematological, Grade 3 or 4	Apply maximum supportive care recommendations (see section Error! Reference source not found.) Hold lapatinib therapy until recovery to Grade \leq 1 (up to 14 days). Refer to events management instructions Section Error! Reference source not found. Grade 3 or 4 left ventricular cardiac dysfunction - please refer to specific section Error! Reference source not found. For NCI-CTCAE v3.0 Grade 3 or 4 interstitial pneumonitis or Grade 4 rash manifested as toxic epidermal necrolysis (e.g. Stevens-Johnson Syndrome etc) lapatinib must be permanently discontinued If recurrence of adverse event after drug hold / interruptions is observed, and maximum supportive care measures applied, a dose reduction by 250mg is recommended. Lapatinib should not be used at doses below 1000mg if given as monotherapy or 750mg in combination with trastuzumab. NOTE: The 750 mg dose should only be used after all supportive measures have been exhausted. (If administered in combination with paclitaxel refer to table 13)
Non-hematological, Grade 3 or 4 and adverse events NOT resolved to Grade \leq 2 within a maximum of 2 weeks from last planned administration	Action (discontinue or resume lapatinib therapy) in individual cases to be decided by the Executive Committee. Dose reductions by 250mg (up to 2 reductions) will be considered after maximum supportive care recommendations (see Error! Reference source not found.) are introduced.

Cardiac* (asymptomatic drop in LVEF or symptomatic congestive heart failure)
	
Lapatinib therapy to be discontinued permanently in case of symptomatic NYHA class III and IV CHF. Lapatinib therapy to be hold continued or resumed according to Figure 1 for patients with NYHA class I or II CHF.

Hematological adverse events: Absolute neutrophil count (ANC) <1.0 x 10⁹/L Platelets <75 x 10⁹/L Hemoglobin <9.0 g/dL (after transfusion if needed)
	
Hold chemotherapy if lapatinib given simultaneously; if the adverse event is related to chemotherapy please refer to appropriate label (until recovery to Grade ≤1). If ANC recovers to 1.5 x 10⁹/L within 7days, then merely delaying dose is acceptable. If no recovery to ANC of 1.5 x 10⁹/L within 7 days then decrease chemotherapy dose by 20%. Dose modifications for thrombocytopenia, at the start of subsequent courses of therapy are the same as recommended for neutropenia above. Next cycle should not begin until the platelet count has recovered to 100 x 10⁹/L or more.

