	
In case of multiple short interruptions of dose due to either adverse events or drug supply or other reasons the sum of days without lapatinib treatment should not exceed 21 days in any 90 day treatment period.

*Severity corresponding to NYHA criteria

RECOMMENDED ELEMENTS OF A SCIENTIFIC PROTOCOL
(Noted sections should only be included as applicable to your research)

29

Dose Delays and Dose Reductions

Treatment may be delayed, up to 2 weeks, to allow for resolution of toxicity except in the event of NCI CTCAE Grade 3 or 4 left ventricular cardiac dysfunction or NCI CTCAE Grade 3 or 4 interstitial pneumonitis (See Criteria for Evaluating Cardiac and Respiratory Events). The Investigator must consult the Novartis Medical Monitor prior to continuing therapy for any subject requiring a delay of more than 2 weeks for unresolved toxicity, but in general, such subjects should be withdrawn from the study. If treatment is delayed for reasons other than toxicity (i.e., unplanned travel or vacation, or lack of transportation to the site) and the subject has insufficient investigational product available, the subject should resume the usual dosing schedule once drug supply has been made available. However, if the subject has been off therapy for more than 2 weeks, the Investigator must consult the Novartis Medical Monitor prior to continuing therapy.

Dose reduction for drug-related toxicity is permitted; however the Novartis Medical Monitor must be consulted prior to implementing any change in dosing. Only one dose reduction is permitted per subject and subjects should not be rechallenged to a higher dose level. If a NCI CTCAE Grade 3 or 4 drug-related event (other than left ventricular cardiac dysfunction or interstitial pneumonitis) has occurred, the investigator may discuss with the Novartis Medical Monitor whether a reduction of dose is appropriate.

PHARMACEUTICAL INFORMATION

Lapatinib (NSC #727989)

Chemical Name: N-{3-Chloro-4-[(3-fluorobenzyl)oxy]phenyl}-6-[5-{{[2-(methylsulfonyl)ethyl]amino}methyl)-2 furyl]-4-quinazolinamine,

Other Names: None

Mode of Action: Dual inhibitor of epidermal growth factor receptor (EGFR or ErbB1) and ErbB2 tyrosine kinases.

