Tumor maximal size will be obtained at baseline, 3 months, 6 months after initiation of treatment. The primary hypothesis is the change from baseline to 6 months. The analysis using maximal resistant tumor size will be carried out for the specified times given above. Initially this will be by descriptive analytic and then by inferential analysis using the test for change between baseline and 6 months and change between baseline and 3 months using rank test. We will also use Hotelling's T^2 to combine both pre-post changes.

This study is in the clinical trials paradigm essentially a Phase IIa trial and thus use of alpha type 1 error is at 10%. This is sanctioned by the biostatistics section of NCI.⁴⁰ We will also analyze the secondary endpoints of Aim 1 according to the above models. Concepts behind analysis for quantitative and binary are the same though the methods are different.

Our overall target sample size is 30 subjects which includes nonfunctioning adenomas and prolactinomas, 15 to be recruited from Cedars Sinai Medical Center and 15 from Johns Hopkins Hospital and Massachusetts General Hospital. We aim to recruit 24 subjects with prolactinomas and 6 nonfunctioning adenomas.

Due to the rarity of pituitary tumors in the general population and even more rare are aggressive pituitary tumors such as we propose to study, it is difficult to do a randomized placebo controlled trial with sufficient sample size numbers to achieve adequate power. By using the subjects as their own controls, we alleviate the issues with recruitment. This is a safety and activity trial to look for a sufficient effect of the drug on tumor growth before proceeding to a larger, randomized placebo controlled trial.

Section 10.0. Quality Control and Quality Assurance

Only samples and data collected with appropriate consent will be used for the proposed analysis. Specimens and data collected under the proof of concept clinical trial of lapatinib will be coded in such a way so that other members of the research team will be unable to ascertain the identity of specific patients. All of our data will be

RECOMMENDED ELEMENTS OF A SCIENTIFIC PROTOCOL
(Noted sections should only be included as applicable to your research)

38

maintained confidentially. Data will be kept in locked file cabinets and in password protected files on computer systems.

Section 11.0 Ethical considerations relating to the trial

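### Follow-up after a toxicity stop is inconsistent: liver stops stay in assessments, while patients off drug more than 2 weeks are generally withdrawn from the study, so the 6-month outcome would probably be missing selectively

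*Combined protocol and SAP*

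**What the plan says.** Section 8.0 deals with what follows a toxicity stop in several places, and they differ.

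- **Liver Chemistry Stopping Criteria.** Patients permanently off drug on these criteria "must continue to be followed for the study assessments and procedures as defined in Section X". The section reference is an unfilled placeholder.
- **Dose Delays and Dose Reductions.** The medical monitor must be consulted before therapy continues in "any subject requiring a delay of more than 2 weeks for unresolved toxicity", and the sentence ends "but in general, such subjects should be withdrawn from the study". The wording is the study, not the drug.
- **Grade 4 toxicity (item 2 of Section 8.0).** Such patients "will be discontinued on the study drug". Follow-up is not mentioned. The cardiac, severe rash and interstitial lung disease rules likewise stop the drug and are silent on follow-up.
- **Table 1, Grade 3 or 4 events not resolved within 2 weeks.** Discontinuing or resuming drug is "in individual cases to be decided by the Executive Committee". Follow-up is again not mentioned.

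On the outcome, Section 7.0 gives "Primary outcome in prolactinomas: 40% reduction in tumor size in any dimension", and Section 9.0 says "The primary hypothesis is the change from baseline to 6 months". Section 9.0 times the measurements at 3 and 6 months from the start of treatment.

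**The concern.** Leaving the study is a different act from stopping the drug. A patient who stops at month 2 on the liver criteria is to remain in assessments. A patient who stops the same day with diarrhea that has not resolved after 2 weeks is, in general, to leave. Nothing in the protocol then provides for that second patient's 6-month MRI.

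The patients lost this way are those who could not tolerate the drug. If they drop out of the analysis, the response rate, the PRL changes and the tumor-volume changes describe mainly those who tolerated it. Section 9.0 presents the trial as a look for activity before a larger randomized trial, and there is no control arm, so that decision would rest on a selected group. The target of 24 prolactinomas also equals the calculated sample size, with no allowance for losses.

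**Working it through.** **1. Is there a safety net?** Section 6.0 introduces the monthly schedule with "While on the drug, visits will occur once a month to monitor for adverse effects". Visit 8, the only off-drug visit, applies only when lapatinib stops at visit 7, and it has no MRI. Data collection after the trial is described only for responders who stay on drug. Section 9.0 names no analysis population and no rule for a missing outcome. The planned Hotelling's T² combines the 3- and 6-month changes, so it needs both MRIs from each patient. That the 6-month outcome would be missing is thus an inference from withdrawal with no planned MRI; no sentence says so.

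**2. Reproduce the plan's figure.** Inputs from Section 9.0: one-sided exact binomial test, null proportion 0.20, alternative 0.40, alpha 0.10, N = 24.

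The cut-off r is the smallest value with P(X ≥ r | n, 0.20) ≤ 0.10. For n = 24:

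- P(X ≥ 7 | 24, 0.20) = 0.189, too large.
- P(X ≥ 8 | 24, 0.20) = 0.089, so r = 8.
- Power = P(X ≥ 8 | 24, 0.40) = 0.808.

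The stated >80% reproduces, and 24 is the smallest N that reaches 80%.

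**3. Losses.** Let m of the 24 patients have no 6-month MRI. The documents do not give m, so 1 to 5 is an assumption. The upper end is set by the 21% rate of Grade 3 and 4 events quoted in Section 8.0 (24 × 0.21 = 5.04). That is an event rate, not a rate of toxicity lasting beyond 2 weeks.

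- Completers-only power: n = 24 − m, r re-derived, P(X ≥ r | n, 0.40).
- Completer rate when the all-treated rate is 0.20 and lost patients do not respond: 0.20 × 24 / (24 − m). For m = 5, 4.8 / 19 = 0.253.
- False-positive chance: P(X ≥ r | n, completer rate).
- Power with missing counted as non-response: 8 of 24 still required, responses only from 24 − m patients at 0.40, so P(X ≥ 8 | 24 − m, 0.40).

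| Lost (m) | n | r | Completers-only power | Completer rate under null | False-positive chance, completers only | Power, missing = non-response |
|---|---|---|---|---|---|---|
| 0 | 24 | 8 | 80.8% | 20.0% | 8.9% | 80.8% |
| 1 | 23 | 8 | 76.3% | 20.9% | 8.8% | 76.3% |
| 2 | 22 | 8 | 71.0% | 21.8% | 8.7% | 71.0% |
| 3 | 21 | 8 | 65.0% | 22.9% | 8.5% | 65.0% |
| 4 | 20 | 7 | 75.0% | 24.0% | 18.4% | 58.4% |
| 5 | 19 | 7 | 69.2% | 25.3% | 18.2% | 51.2% |

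The jump between 3 and 4 losses occurs because the cut-off falls from 8 to 7. In the last column the all-treated response rate is itself below 40%: with m = 5 it is 0.40 × 19 / 24 = 31.7%.

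**The case against.** Most toxicity rules in Section 8.0 stop only the drug. The Dose Delays sentence is the outlier, and it is softened by its own qualifier and by the consultation with the medical monitor. This stands, and it limits the point: a reader might infer that the protocol treats stopping drug and leaving the study as one act everywhere outside the liver section, but the Grade 4, cardiac, rash and lung rules do not say that. They say nothing about follow-up, which leaves sites to differ.

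A reader might also infer that all visits and MRIs are defined by time on drug. The visit headings in Section 6.0 read that way, but the flowsheet counts calendar days and Section 9.0 counts from the start of treatment. A patient who stops after visit 4 already has the 3-month MRI, and PRL is measured monthly in prolactinomas.

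The size is open as well. A reader might take the 21% as the rate of loss, or 18% as the false-positive rate. Section 8.0 also provides for Grade 3 events to be held and resumed, and gives no rate for toxicity beyond 2 weeks. With 1 to 3 losses there is no false-positive inflation. A completers-only analysis is itself an assumption, since the plan specifies none.

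Finally, counting missing as non-response costs more power than completers-only analysis at 4 or 5 losses (51.2% against 69.2% at 5). That stands, and it is the reason to collect the MRIs rather than rely on the counting rule.

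**Conclusion.** The point holds in limited form. The rules on follow-up after a toxicity stop conflict or are silent, and nothing provides for the 6-month MRI of a patient withdrawn for unresolved toxicity. The primary outcome would probably be missing selectively in intolerant patients.

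The most robust consequence is for power: with completers responding at 40%, a single missing outcome takes it to 76.3%, and 1 to 5 losses give 65.0% to 76.3%. The upward shift of the completer rate, to between 20.9% and 25.3% from a true 20%, assumes that no lost patient would have responded. A false-positive chance of about 18% needs that assumption, a completers-only analysis and 4 or 5 losses together. The documents do not supply the number lost, so these are ranges, not predictions. The point concerns follow-up and missing data; it makes no judgement on when the drug should be stopped.

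**What to change.** 1. Reconcile the Grade 4 rule, the Liver Chemistry Stopping Criteria, Table 1 and Dose Delays and Dose Reductions, so that stopping study drug is separate from leaving study follow-up. Fill the placeholder reference in the liver text. Leave every rule on when drug is stopped or resumed as it is.
2. State that patients who stop drug for toxicity and have not withdrawn consent keep the 3- and 6-month MRI and PRL, timed from the start of treatment as Section 9.0 already has it.
3. In Section 9.0, base the responder analysis on all treated patients, count a missing 6-month MRI as non-response, and add a completers analysis as sensitivity.
4. Describe the stated >80% power as assuming no losses.

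Cost: the MRIs and PRL tests are already scheduled, but some visits will take place off drug, and Section 13.0 charges patients for hormonal tests during the study, so who pays for off-drug PRL needs settling. The reported response rate will be lower, and so will power if stoppers do not respond (51% with 5 such patients).

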Trial design: Open label, single cohort proof of concept trial. An additional arm of the study will be for subjects treated with the study drug in malignant pituitary tumors. Three clinical trial sites, one at CSMC and the others at Johns Hopkins Hospital and Massachusetts General Hospital.

Study population: Patients will be recruited from the Pituitary Center at Cedars-Sinai Medical Center and the other two sites.

Intervention: lapatinib 1250 mg daily for 6 months. Patients will be treated with the standardized dose used in breast cancer therapy for six months (Cameron & Stein 2008; Geyer et al. 2006). The drug will be supplied by Novartis Oncology.

- a. Primary outcome variable.

Primary outcome in nonfunctioning pituitary adenomas: 40% reduction in tumor size in any dimension. Tumor size and volume will be calculated using Open Source OsiriX® Imaging Software for MacOS. MRIs will be performed at baseline and at 3 and 6 months All MRIs will be centrally read by the dedicated pituitary radiologist at CSMC.

Primary outcome in prolactinomas: 40% reduction in tumor size in any dimension.

Primary outcome in malignant pituitary tumors: Progression free survival

- b. Secondary outcome variables.

Secondary outcomes in prolactinomas:

(a) achievement of 50% reduction of PRL levels (b) PRL normalization (c) percent reduction in PRL levels (d) percent reduction in tumor volume. Tumor volume will be calculated using Open Source OsiriX® Imaging Software for MacOS. (e) correlation of tumor size and PRL reduction (f) clinical predictors of TKI response, including age, gender, duration of disease, dose and duration of dopamine agonist therapy, baseline PRL, and baseline tumor size.

Secondary outcomes in malignant pituitary tumors: partial response, complete response, mortality, 24 hour urine free cortisol levels for Cushing carcinomas, IGF-1 levels for acromegaly carcinomas.

We will correlate ErbB receptor expression with the subjects' clinical response to the study drug. This will be performed through immunohistochemistry staining of pituitary tumor slides from surgery.

Section 5.0. Selection and Withdrawal of Subjects

Inclusion criteria: Subjects with non-functioning pituitary adenomas, who have undergone at least one prior surgical resection and have demonstrated recurrence on MRI.

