For any other NCI-CTCAE v3.0 Grade 3 or 4 adverse events or any clinically significant, lower-grade adverse event, treatment with lapatinib should be interrupted for a maximum of 14 days until the patient recovers completely or the adverse event reverts to NCI-CTCAE v3.0 Grade 1 or to baseline grade. If recurrence of adverse event after drug holiday / interruptions is observed a dose reduction by 250mg is recommended. Dose reduction should only be implemented when all supportive care measures have been exhausted without an improvement of patient status. Lapatinib should not be used at doses below 1000mg if given as monotherapy or 750mg in combination with trastuzumab. In all cases where the subject is withdrawn due to unusual or unusually severe adverse event considered related to lapatinib, the investigator must report the withdrawal as an SAE and on the CRFs.

Table 1 Summary of dose holding/interruptions and dose de-escalation recommendations for GW572016 (lapatinib) in case of lapatinib related adverse events (graded according to NCI-CTCAE v3.0)

Adverse events	Action
Non-hematological, Grade 1 or 2	Continue lapatinib therapy at full dose prescribed (see adverse events management instructions section Error! Reference source not found. Apply maximum supportive care recommendations (see Error! Reference source not found.) If prolonged duration of Grade 2 adverse event is affecting quality of life a one-time decrease of dose by 250 mg is allowed.

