How Supplied: lapatinib is supplied as 250 mg oval, biconvex, orange film-coated tablets with one side plain and the opposite side debossed with FG HLS. The tablets contain 410 mg of lapatinib Ditosylate Monohydrate, equivalent to 250 mg lapatinib free base per tablet. The tablets are packaged into HDPE bottles with child-resistant closures.

Excipients present in the tablet include: Microcrystalline cellulose, povidone, sodium starch glycolate, and magnesium stearate.

The film-coat contains: Hydroxypropyl methylcellulose, titanium dioxide, triacetin/glycerol triacetate, and yellow iron oxide.

Storage: The intact bottles should be stored at controlled room temperature (15°C-30°C).

Stability: Shelf life surveillance studies of the intact bottle are on-going. Current data indicates lapatinib is stable for at least 2 years at controlled room temperature (15°C - 30°C).

RECOMMENDED ELEMENTS OF A SCIENTIFIC PROTOCOL
(Noted sections should only be included as applicable to your research)

Route of Administration: Oral on an empty stomach (either 1 hour before or 1 hour after meals).

Kool-Aid Flavored Suspension

Prepare Lemonade or Tropical Punch Kool-Aid as directed on the package. Place 2 or 4 oz of Kool-Aid (room temperature or refrigerated) in a glass container, then add six 250 mg lapatinib tablets to the container. Cover the container, let it stand for 5 minutes, and then stir the mixture intermittently for 10-20 minutes or until the tablets are completely broken up. Stir the container for 5 seconds then administer. Rinse the container with a 2 oz aliquot of water and administer (total of 4-6 oz of liquid is dispensed).

Suspension in Water

Place 4 oz of water in a glass container, then add six 250 mg lapatinib tablets to the container. Cover the container, let it stand for 5 minutes, and then stir the mixture intermittently for 10-20 minutes or until it is fully dispersed. Stir the container for 5 seconds then administer. Rinse the container with a 2 oz aliquot of water and administer (total of 6 oz of liquid is dispensed).

Prohibited Medications

Lapatinib is a substrate for CYP3A4. Inducers and inhibitors of CYP3A4 may alter the metabolism of lapatinib. The following list of CYP3A4 inducers and inhibitors are prohibited from screening through discontinuation from study.

Drug Class	Specific Agents	Wash-out ¹
CYP3A4 Inducers		
rifamycin antibiotics	rifampicin, rifabutin, rifapentine	2 weeks

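### Both suspension recipes call for six 250 mg tablets (1500 mg), 20% above the trial dose of 1250 mg daily

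*Combined protocol and SAP*

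**What the plan says.** Section 4.0 (Trial Design) gives one dose for every patient: "Intervention: lapatinib 1250 mg daily for 6 months". It describes this as the standardized breast cancer dose.

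In Section 8.0, under Pharmaceutical Information, the How Supplied paragraph gives the tablet strength as "equivalent to 250 mg lapatinib free base per tablet".

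The Route of Administration text that follows has two suspension recipes, and both contain the same instruction, "then add six 250 mg lapatinib tablets to the container":

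- Flavoured drink: 2 or 4 oz of liquid at "room temperature or refrigerated) in a glass container, then add six 250 mg lapatinib tablets to the container".
- Water: "Place 4 oz of water in a glass container, then add six 250 mg lapatinib tablets to the container".

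Both then have the mixture stirred and given, and the container rinsed and the rinse given. The water recipe ends: "Rinse the container with a 2 oz aliquot of water and administer (total of 6 oz of liquid is dispensed".

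Neither recipe names a dose in milligrams, refers back to Section 4.0, or changes the tablet count for a patient whose dose has been reduced.

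**The concern.** The protocol gives two incompatible amounts for what should be the same daily dose. A pharmacist, nurse or patient following the recipe exactly would give a dose that the protocol does not define.

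Three things are at stake:

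- **Patient safety.** The excess falls on a drug for which Section 8.0 itself lists reduced ventricular function, QT prolongation and hepatotoxicity as rare but serious risks.
- **Reduced-dose patients.** Because the recipe is fixed at six tablets, a patient already reduced for toxicity would go above the starting dose if switched to suspension.
- **Interpretation.** Section 9.0 plans 30 patients (24 prolactinomas and 6 nonfunctioning adenomas) and calls the study a safety and activity trial. In a group that small, a few patients at an unplanned higher dose would blur which dose the toxicity and response results describe.

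**Working it through.** **Inputs**

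| Quantity | Value | Source |
|---|---|---|
| Protocol dose | 1250 mg daily | Section 4.0, Intervention |
| Tablet strength, free base | 250 mg | Section 8.0, How Supplied |
| Tablets per suspension | 6, in both recipes | Section 8.0, Route of Administration |
| Monotherapy floor after reduction | 1000 mg | Section 8.0, Other adverse events and Table 1 |

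**Step 1: the protocol dose in tablets.** 1250 / 250 = 5 tablets.

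**Step 2: the dose the recipe delivers.** 6 × 250 = 1500 mg.

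**Step 3: the difference.** 1500 − 1250 = 250 mg; 1500 / 1250 = 1.20, so +20%.

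**Step 4: could a smaller dose be intended?**

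- *Salt against base.* No. The 250 mg is already free base; the salt weight is given separately as 410 mg.
- *A stock mixture with part held back.* No. In the water recipe, 4 oz prepared plus 2 oz rinse equals the 6 oz stated as dispensed. In the flavoured recipe, 2 or 4 oz plus 2 oz equals the stated 4 to 6 oz. Everything prepared is given.
- *Another permitted dose level.* No. The dose-modification text only goes down, and its lower limit reads "Lapatinib should not be used at doses below 1000mg if given as monotherapy". Nothing allows 1500 mg.
- *A reading error in one place.* Unlikely. The count is spelled out as a word and is the same in both recipes.

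**Step 5: patients on a reduced dose.** The excess depends on which reduction rule applies, because Section 8.0 contains more than one:

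| Rule in Section 8.0 | Assigned dose | Tablets needed | Recipe / assigned dose |
|---|---|---|---|
| One 250 mg step (Other adverse events; Table 1) | 1250 − 250 = 1000 mg | 4 | 1500 / 1000 = 1.50 (+50%) |
| Fifty percent cut after Grade 3 toxicity (item 2 of the monitoring list) | 1250 × 0.5 = 625 mg | 2.5 | 1500 / 625 = 2.40 (+140%) |

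The second rule also falls below the 1000 mg floor and does not correspond to a whole number of tablets. The first row is therefore the more workable comparison, and the second marks the upper end.

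**The case against.** The best case on the other side accepts the arithmetic and disputes how far it reaches.

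- **Nobody may use a suspension.** The drug is supplied as tablets, the visit schedule has no suspension step, the advice on vomiting speaks of tablets, and eligibility does not single out patients who cannot swallow them. This stands. It makes the 20% conditional on use, but it does not make the instruction correct.
- **The text looks like leftover generic drug information.** Nearby pages refer to trastuzumab, paclitaxel, platinum-induced nausea and an executive committee, none of which belongs to this study. That is a plausible origin, though the documents do not confirm it. The page header says sections should be included only where applicable, so a reader is entitled to treat the recipes as live.
- **The protocol already guards reduced-dose patients.** The Dose Delays and Dose Reductions text bars going back to a higher level and requires the medical monitor to be consulted before any change in dosing. Both are real safeguards. They also mean that the recipe, followed literally, breaks those rules, so the contradiction remains.
- **Exposure was never a single dose.** Holds, reductions and restarts are allowed, so it would be too strong to say that only the recipe prevents the data from describing one dose. The narrower point holds: those variations are defined and downward, whereas 1500 mg is undefined and upward.
- **The statistics are untouched.** The endpoint definitions, sample size and tests do not depend on this text. That is right; the case for correction rests on dosing safety and on knowing what dose was studied.

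**Conclusion.** The point holds. Both suspension recipes give 1500 mg where the protocol dose is 1250 mg: an excess of 250 mg, or 20%, on each day a patient takes the full-dose suspension as written. For a patient reduced by 250 mg to 1000 mg the excess is 50%; under the conflicting fifty percent rule it would be 140%.

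The 20% rests only on stated figures and on the recipe being followed literally. The reduced-dose figures additionally assume that the recipe overrides the bar on returning to a higher dose. The number of patients affected is not stated and may be none. The documents give no toxicity or response data at 1500 mg, so the harm cannot be quantified beyond the departure from the assigned dose. Because this is an overdose written into preparation instructions and costs almost nothing to remove, it must be fixed.

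**What to change.** The sponsor and the medical monitor should confirm that 1250 mg is the intended dose for every formulation, then choose one of two changes:

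1. **If suspension is intended for this trial,** replace the fixed count in both recipes with the number of 250 mg tablets equal to the patient's currently assigned dose, with examples: five at 1250 mg and four at 1000 mg. Record on the case report form when a dose is given as suspension, so that exposure can be described. The two dose-reduction rules in Section 8.0 should be reconciled at the same time, since a 625 mg dose cannot be made from whole tablets.
2. **If suspension is not intended,** delete both recipes.

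Either way, the cost is one wording correction by amendment and a pharmacy note to the three sites. If the trial has already dosed patients, ask sites whether any suspension was prepared and with how many tablets. Sample size, endpoints and analysis are unaffected.
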